## **4 Study Enrollment and Withdrawal**

### **4.1 Inclusion Criteria**

In order to be eligible to participate in this study, an individual must meet all of the following criteria:

1. Patient are current candidates for elective primary total hip or total knee arthroplasty
2. Patients  $\geq 18$  years of age but  $\leq 95$
3. Patients have been medically cleared and scheduled for surgery

#### **4.2 Exclusion Criteria**

An individual who meets any of the following criteria will be excluded from participation in this study:

- Non-elective conversion arthroplasty
- Consistent melatonin use within 1 month of surgery
- Bilateral total joint arthroplasty
- Contraindications to use of melatonin (diabetes, calcium channel blocker use, depression)
- Conditions and medications likely to confound results due to impact on subjective and/or objective sleep quality (insomnia, drug/alcohol abuse, and use of benzodiazepines, and prescription sleep aids)
- Conditions likely to impair capacity to adhere to protocol (mental impairment, psychiatric disorders other than anxiety/depression)

#### **4.3 Vulnerable Subjects**

No Vulnerable subjects will be enrolled in this study

#### **4.4 Duration of Study Participation**

Participants will be enrolled for approximately 2months after surgery.

#### **4.5 Total Number of Participants and Sites**

252 patients will be recruited at NYU Langone Orthopedic Hospital and NYU Brooklyn Hospital.

#### **4.6 Participant Withdrawal or Termination**

##### **4.6.1 Reasons for Withdrawal or Termination**

Participants are free to withdraw from participation in the study at any time upon request. An investigator may terminate participation in the study if:

- Any clinical adverse event (AE), laboratory abnormality, or other medical condition or situation occurs such that continued participation in the study would not be in the best interest of the participant

##### **4.6.2 Handling of Participant Withdrawals or Termination**

Any patient that wishes to withdraw or in whom a clinical adverse effect is noticed, will be allowed to do so without recourse. They will still be given appropriate standard of care follow-up as would be given any pre- or post-operative TJA patient. If a patient is presumed lost to follow-up they will be contacted via phone-calls and certified letters, which will be tracked. There is no safety risk predicted from abrupt termination. Any patients who withdraw or discontinue early will be replaced via recruitment of new patients. As LOH is a high-volume arthroplasty center performing thousands of primary TJA procedures there is not expected to be an issue in recruiting new subjects as approximately 10-50% of patients are projected to be affected by malnutrition (previously cited data).

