## Protocol Summary

Title	MELATONIN USE AFTER PRIMARY TOTAL JOINT ARTHROPLASTY: A RANDOMIZED, DOUBLE BLIND, PLACEBO-CONTROLLED TRIAL
Brief Summary	The purpose of this study is to determine the effect of melatonin supplementation on patient sleep quality, length of stay, and opioid consumption following primary, unilateral, elective total hip or knee arthroplasty.
Phase	N/A
Objectives	The primary objective is improved sleep quality postoperatively
Methodology	Single Center, randomized, double-blind, placebo-controlled clinical trial
Endpoint	The primary endpoint will be enrollment and completion of the study of 256 patients as pre-determined by statistical analysis.
Study Duration	Approximately 12 months (post IRB approvals)
Participant Duration	We estimate each patient will need to participate for roughly 60 days
Duration of IP administration	Patients will take the melatonin or placebo for 14 days
Population	Sample size will be 252 patients, both male and female patients will be included, all adult patients undergoing primary elective TKA or THA will be included. No vulnerable populations will be enrolled
Study Sites	Langone Orthopedic Hospital, New York, NY NYU Brooklyn Hospital, Brooklyn, NY
Number of participants	256 participants
Description of Study Agent/Procedure	Melatonin is an over-the-counter sleep aid
Reference Therapy	None
Key Procedures	Pre- and postoperative sleep survey, survey on quality of sleep, patient reported outcome questionnaires, narcotic consumption and pain daily for 14 days postoperatively
Statistical Analysis	Descriptive statistics will be used to report baseline characteristics and primary study objectives

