### **6.2.4 Withdrawal/Early Termination Visit**

If a patient wishes to terminate early no further procedures or interventions will be performed and the patient will be allowed to continue their pre- or post-operative care as per standard of care

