## **8.3 Analysis Datasets**

All patients will be included in the efficacy analyses as randomized (intent-to-treat population). THA cohort and TKA cohort will be analyzed separately throughout.

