## **8.4 Description of Statistical Methods**

### **8.4.1 Analysis of the Primary Efficacy Endpoint**

The primary outcome, the ESS score measured at days 1-14 postoperatively for each group, will be summarized using means, standard deviation, median and inter quartile ranges. In the main analysis, the ESS score of the control and intervention group in either THA or TKA cohort will be compared using repeated measures ANOVA. Significant tests will be two-sided at significant level at 0.05.

The normality assumption of the primary efficacy outcome will be checked and strategies to transform the outcome variable will be considered. As a sensitivity analysis, the ANOVA will be replaced with the Wilcoxon rank sum test to ensure the robustness of the results.

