## **9 Source Documents and Access to Source Data/Documents**

Source data is all information, original records of clinical findings, observations, or other activities in a clinical trial necessary for the reconstruction and evaluation of the trial. Source data are contained in source documents. Examples of these original documents, and data records include: hospital records, clinical and office charts, laboratory notes, memoranda, subjects' diaries or evaluation checklists, pharmacy dispensing records, recorded data from automated instruments, copies or transcriptions certified after verification as being accurate and complete, microfiches, photographic negatives, microfilm or magnetic media, x-rays, subject files, and records kept at the pharmacy, at the laboratories, and at medico-technical departments involved in the clinical trial. It is acceptable to use CRFs as source documents. If this is the case, it should be stated in this section what data will be collected on CRFs and what data will be collected from other sources.

The study case report form (CRF) is the primary data collection instrument for the study. All data requested on the CRF must be recorded. All missing data must be explained. If a space on the CRF is left blank because the procedure was not done or the question was not asked, write "N/D". If the item is not applicable to the individual case, write "N/A". All entries should be printed legibly in black ink. If any entry error has been made, to correct such an error, draw a single straight line through the incorrect entry and enter the correct data above it. All such changes must be initialed and dated. DO NOT ERASE OR WHITE OUT ERRORS. For clarification of illegible or uncertain entries, print the clarification above the item, then initial and date it.

Access to study records will be limited to IRB-approved members of the study team. The investigator will permit study-related monitoring, audits, and inspections by the IRB/EC, the sponsor, government regulatory bodies, and University compliance and quality assurance groups of all study related documents (e.g. source documents, regulatory documents, data collection instruments, study data etc.). The investigator will ensure the capability for inspections of applicable study-related facilities (e.g. pharmacy, diagnostic laboratory, etc.).

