## **10 Quality Assurance and Quality Control**

QC procedures will be implemented beginning with the data entry system and data QC checks that will be run on the database will be generated. Any missing data or data anomalies will be communicated to the site(s) for clarification/resolution.

Following written SOPs, the monitors will verify that the clinical trial is conducted and data are generated, documented (recorded), and reported in compliance with the protocol, GCP, and the applicable regulatory requirements (e.g., Good Laboratory Practices (GLP), Good Manufacturing Practices (GMP)).

The investigational site will provide direct access to all trial related sites, source data/documents, and reports for the purpose of monitoring and auditing by the sponsor, and inspection by local and regulatory authorities.

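### The repeated-measures ANOVA has no way to include patients with incomplete ESS, so the promised as-randomised analysis can become one of completers plus replacements

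*Combined protocol and SAP*

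**What the plan says.** - **Who is analysed.** Section 8.3: "All patients will be included in the efficacy analyses as randomized (intent-to-treat population"). The hip and knee cohorts are analysed separately.
- **How.** Section 8.4.1: in each cohort the ESS of the two groups "will be compared using repeated measures ANOVA". The only sensitivity analysis is that "the ANOVA will be replaced with the Wilcoxon rank sum test to ensure the robustness of the results"; it follows directly on the normality check.
- **Leavers.** Section 4.6.2: "Any patients who withdraw or discontinue early will be replaced via recruitment of new patients". Section 6.2.4: "If a patient wishes to terminate early no further procedures or interventions will be performed".
- **Target.** The Protocol Summary says "The primary endpoint will be enrollment and completion of the study of 256 patients as pre-determined by statistical analysis". Section 8.2 derives 64 per arm and 128 per cohort, with no dropout allowance.
- **Missing data.** Section 9: "All missing data must be explained". Section 10: "Any missing data or data anomalies will be communicated to the site(s) for clarification/resolution". Both govern record-keeping and data queries.
- **ESS schedule.** Sections 3.2.1, 8.1 and 8.2 refer to post-operative days 1-14. The table in 6.2 lists the Epworth scale only at Surgery and Visit 2. In 6.1.1 only the sleep diary is described as daily.

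**The concern.** Section 8.3 settles who belongs in the analysis. It does not settle how someone with a partial ESS series enters the test named in 8.4.1. A classical repeated-measures ANOVA needs every time point and deletes patients who lack one. The Wilcoxon test does not help: it addresses non-normality, and it needs one value per patient with no rule for forming that value from a partial series.

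Sections 6.2.4 and 4.6.2 add to this. Collection stops when a patient leaves, and a new patient restores the count. An analyst could report completers plus replacements, or a model that keeps every partial record, and claim to have followed the plan either way. That choice should not stay open until results are visible.

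Replacement restores numbers but not the randomised comparison. If stopping is related to ESS and differs between arms in rate or reason, a completers' comparison is biased. Deleting incomplete patients also discards the days they did report.

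**Working it through.** **Inputs from section 8.2.** Difference 2.65, SD 5.3, two-sided alpha 0.05, 64 per arm. All dropout and missed-day rates below are assumptions.

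**1. The plan's own figure.** Standardised difference 2.65/5.3 = 0.5. A two-sample t test (noncentral t) with 64 per arm has power 80.1%. The stated sample size reproduces.

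**2. Bias of a completers' comparison.** Let a proportion q of an arm stop, and let stoppers' ESS differ from completers' by d. The completers' mean is then off by q × d in that arm, and the comparison is off by qT·dT − qC·dC. Replacement is assumed to restore 64 completers per arm. Type I error and power use noncentrality (shift/5.3) × √(64/2). The last column applies if the bias runs against melatonin.

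| Stopping, melatonin vs placebo | d (points) | Bias (points) | Share of 2.65 | Type I error | Power |
|---|---|---|---|---|---|
| 10% vs 10%, same reasons | 2.65 | 0 | 0% | 5.0% | 80% |
| 10% vs 5% | 2.65 | 0.05 × 2.65 = 0.13 | 5% | 5.2% | 76% |
| 15% vs 5% | 2.65 | 0.10 × 2.65 = 0.27 | 10% | 5.9% | 71% |
| 15% vs 5% | 5.3 | 0.10 × 5.3 = 0.53 | 20% | 8.7% | 61% |

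Equal rates do not guarantee zero bias. With 10% stopping in both arms but d = 2.65 in one arm and 0 in the other, the bias is again 0.27.

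**3. Power if incomplete patients are deleted, at an assumed 2% missing, with 5.3 as the SD of the analysed endpoint.**

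| Pattern | Complete | Patients per arm | Power |
|---|---|---|---|
| Whole patients missing | 0.98 | 62.7 | 79.3% |
| Two visits, missed independently | 0.98² = 0.960 | 61.5 | 78.5% |
| Fourteen days, missed independently | 0.98¹⁴ = 0.754 | 48.2 | 68.1% |

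If 5.3 is instead a single-day SD, the SD of a 14-day mean is 5.3 × √((1 + 13r)/14), where r is the within-patient correlation. At r = 0.9 (SD 5.05), power falls from 84% to 83% with whole patients missing, or to 72% with days missed independently. At r = 0.7 (SD 4.50), it falls from 91% to 91% (a loss of under 1 point) or to 82%. In the independent-days case, a mixed model using all observed days keeps 84% and 91%.

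**4. Does a mixed model remove the bias?** A simulation took a true effect of zero, r = 0.7, 64 per arm, and stopping after day 3 with probability depending on mean ESS over days 1-3. With 15% vs 5% stopping and stoppers about 3.0 points higher, completers gave bias −0.27 and 6.6% rejection; a compound-symmetry mixed model gave +0.03 (Monte Carlo SE 0.013) and 5.3%. Stopping there depends only on observed scores, so the data are missing at random by construction. The result says nothing about patients who leave before any post-operative ESS, or who stop for unobserved reasons.

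**The case against.** **Intent-to-treat is already promised.** This largely stands. A reader might infer that replacement itself breaches intent-to-treat, or that replaced patients are to be excluded. The documents do not support that. Section 8.3 read literally covers both the patient who left and the one added, no section drops a leaver's data, and 11.4 allows use of data collected before authorisation is revoked. Taking the next block allocation is also the natural reading of 8.5.1 for a new recruit. What remains is that 8.3 gives no mechanism for incomplete series.

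**The ANOVA might be fitted as a mixed model.** It might, and partial records would then be kept. Section 8.4.1 does not say so.

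**The Summary is a weak basis for a completers' quota.** Agreed. That field describes recruitment as an endpoint, and 4.5 speaks only of recruiting 252. The point does not depend on it.

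**The rates are speculative.** Also fair. Section 1.4.1 describes adverse effects as mild, and dosing lasts 14 days, so threefold differential stopping is not an expected case. The smallest unequal scenario barely moves type I error.

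**Missingness could be examined anyway.** In part: reasons are to be recorded (section 9), contacts with patients lost to follow-up are tracked (4.6.2), and individual data are listed (8.4.8). Stopping by arm could be tabulated from these, but no such table and no sensitivity analysis for missing ESS is planned.

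**Conclusion.** The gap is real and should be fixed. The test named in 8.4.1, in its classical form, cannot deliver what 8.3 promises, and nothing else in the plan says how missing ESS is analysed. This is a risk, not a planned error.

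Its size cannot be fixed from the documents. Bias is zero if stopping is equal in rate and reason. Under the assumed differential scenarios, type I error lies between about 5.2% and 8.7%.

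A reader might take the fall in power to 68% as the expected consequence. The documents do not support that: it needs daily ESS, days missed independently at 2%, and deletion of incomplete patients all at once, and the table in 6.2 does not schedule daily ESS. If whole patients are missing, or ESS is collected at two visits, the loss at 2% is about 1 to 2 points. Confidence is high that the rule is missing, and much lower about how much harm follows.

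**What to change.** 1. **Primary model (8.4.1).** First reconcile the ESS schedule between 3.2.1, 8.1 and 8.2 (days 1-14) and 6.2 (Surgery and Visit 2). Then, within each joint cohort, replace the ANOVA with a likelihood-based linear mixed model on all available post-operative ESS values, with treatment, time and treatment-by-time. Prespecify the covariance structure and one treatment contrast consistent with 8.1. Section 8.1 needs a clear choice here: its null concerns the mean over days 1-14, while its alternative refers to any of the time points.
2. **Replacement (4.6.2 and 8.3).** State that added patients are new randomisations, and that everyone randomised, including those replaced, stays in the assigned arm with all data collected.
3. **Data collection (6.2.4).** Separate stopping study pills from withdrawing consent, and keep collecting ESS and the diary from patients who only stop pills. Sections 6.2.3 and 8.4.4 record adherence, so imperfect pill-takers already appear to stay in; this makes it explicit. It concerns data collection only.
4. **Sensitivity analysis.** Add one analysis for departures from missing at random, such as a delta shift applied separately by arm, reporting where the conclusion changes.

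The covariance structure, degrees-of-freedom method and delta step are the sponsor's choice. If ESS is daily, an unstructured 14-day matrix would have 14 × 15/2 = 105 parameters for 128 patients, so a simpler structure is sensible.

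**Cost.** Wording in four sections, one reconciled schedule row, a standard model and one extra analysis. Patients who stop pills answer a few more questionnaires. The mixed model relies on missing at random, which item 4 tests.

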#### **4.7 Premature Termination or Suspension of Study**

This study may be temporarily suspended or prematurely terminated if there is sufficient reasonable cause. Written notification, documenting the reason for study suspension or termination, will be provided

by the suspending or terminating party to the IRB. If the study is prematurely terminated or suspended, the PI will promptly inform the IRB and will provide the reason(s) for the termination or suspension. Circumstances that may warrant termination or suspension include, but are not limited to:

- Determination of unexpected, significant, or unacceptable risk to participants
- Insufficient compliance to protocol requirements
- Data that are not sufficiently complete and/or evaluable

Study may resume once concerns about safety, protocol compliance, data quality are addressed and satisfy the IRB.

## **5 Study Agent (Study drug, device, biologic, vaccine etc.) and/or Procedural Intervention**

### **5.1 Study Agent(s) and Control Description**

Melatonin, as previously described, is a widely available over the counter sleep aid.

#### **5.1.1 Acquisition**

Melatonin will be ordered in bulk from a generic retail option that can be found. Once ordered it will be shipped via standard US mail. It will be distributed to the patient during the pre-operative booking appointment. Placebo pills will also be ordered in similar fashion. Melatonin and placebo pills will be re-packaged in the new blank pill bottles with a generic label with dosage instructions by the research coordinator. Only the unblinded research coordinator, will know which bottles correspond to the treatment group.

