## **3 Study Design and Endpoints**

### **3.1 Description of Study Design**

This will be a single-center randomized double blind placebo control clinical trial. In the cohort of patients undergoing primary elective total hip and the cohort of patients undergoing primary elective knee arthroplasty, participants are recruited from those who are willing to consent and participate in the study, and will be randomly 1:1 divided into intervention group and placebo group.

Knee cohort:

- Intervention group will receive a 5mg Melatonin prescription for 14 days
- Control group will receive a placebo pill for 14 days

Hip cohort:

- Intervention group will receive a 5mg Melatonin prescription for 14 days
- Control group will receive a placebo pill for 14 days

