#### **5.1.2 Formulation, Appearance, Packaging, and Labeling**

Melatonin is a widely sold synthetic molecule in various forms including tablets, gummies and liquid. In the present study, the tablet version of the medication will be used at a dose of 5mg. It will be distributed to patients in a standard pill pack labelled as "Study Drug." Patients will be informed that they will either be taking melatonin or a placebo pill with no chemical activity. Only the research staff involved in the randomization process will know if the patient is in the melatonin arm or the placebo arm. The placebo ingredients are Microcrystalline Cellulose, Silica, Gelatin, Titanium Dioxide, Red #3, and Blue #1.

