### 6.2.1 Screening

Study subjects will be identified/recruited by all study investigators. Investigators will recruit subjects among their own patients who have been recommended to have a Total Hip or Knee Arthroplasty. Eligibility will be confirmed through a review of subject medical records. Investigators will reinforce with their patients that participation is voluntary, that they do not have to participate, and that their decision to not participate will not affect their care, now or in the future. During the course of the recruitment process, subjects will interact with all study personnel.

With access granted by MCIT, Study team will access data/records in EPIC for patients identified by study investigators as meeting the study criteria.

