## **8.5 Measures to Minimize Bias**

### **8.5.1 Enrollment/Randomization/Masking Procedures**

Research assistants not involved in the study protocol will be responsible for maintaining the patient database and randomization algorithm. Treatment will begin on postoperative day zero. The control groups will receive 14 placebo pills. The treatment group will receive 14 pills of 5mg melatonin. Patients will begin taking a daily pill for 14 days postoperatively. They will continue to receive their selected treatment during their inpatient hospital stay.

Block randomization will be done through RedCap to ensure equal distribution of intervention vs control subjects. The block size will be undisclosed. There will be no stratification based on age, gender, or surgery type.

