#### **11.3.2 Consent Procedures and Documentation**

Informed consent is a process that is initiated prior to the individual's agreeing to participate in the study and continues throughout the individual's study participation. Extensive discussion of risks and possible benefits of participation will be provided to the participants and their families. Consent forms will be IRB-approved and the participant will be asked to read and review the document.

The informed consent process will take place at a pre-surgery clinic visit prior to the day of surgery or in the holding area on the day of surgery. If consenting occurs on the day of surgery, the study team will ensure that efforts are made so patients have enough time to make an informed decision to enroll in the study. A study coordinator, not associated with the surgery, will be the one to introduce the study to the patient in the holding area and patients will be given the opportunity to enroll in the study after the surgery is complete.

The Informed Consent Form (ICF) will be thoroughly explained in a private room with any and all questions addressed prior to signing the ICF. In the event additional time to make an informed decision is required, patient(s)/subject(s) will be able to take a copy of the ICF home for further review and discussion with their friends and family. During the course of the consenting process, subjects will interact with all study personnel. The participant will sign the informed consent document prior to any procedures being done specifically for the study. The participants may withdraw consent at any time throughout the course of the trial. A copy of the signed informed consent document will be given to the participants for their records. The rights and welfare of the participants will be protected by emphasizing to them that the quality of their medical care will not be adversely affected if they decline to participate in this study.

A copy of the signed informed consent document will be stored in the subject's research record. The consent process, including the name of the individual obtaining consent, will be thoroughly documented in the subject's research record. Any alteration to the standard consent process (e.g. use of a translator, consent document presented orally, etc.) and the justification for such alteration will likewise be documented.

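### The stated procedures do not secure the double blind: nothing requires the two pills to look alike, and the unblinded role is named inconsistently and not kept apart from recruitment

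*Combined protocol and SAP*

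**What the plan says.** The design claim in section 3.1 is: "This will be a single-center randomized double blind placebo control clinical trial".

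**The product.** Under 5.1.1 the melatonin is bought in bulk from whatever generic retail source is found, and the placebo is bought in the same way. The research coordinator moves both into blank bottles with a generic label. Section 5.1.2 fixes the melatonin as a 5 mg tablet and says of the other product: "The placebo ingredients are Microcrystalline Cellulose, Silica, Gelatin, Titanium Dioxide, Red #3, and Blue #1". Its heading includes appearance, but it gives no color, shape, size or marking for either pill.

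**Who is unblinded.** Three sections answer this differently.
- 5.1.1: "Only the unblinded research coordinator, will know which bottles correspond to the treatment group".
- 5.1.2: "Only the research staff involved in the randomization process will know if the patient is in the melatonin arm or the placebo arm".
- 8.5.1: "Research assistants not involved in the study protocol will be responsible for maintaining the patient database and randomization algorithm".

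**Who meets patients.**
- 6.2.1: "During the course of the recruitment process, subjects will interact with all study personnel".
- 11.3.2: "During the course of the consenting process, subjects will interact with all study personnel". For consent on the day of surgery it adds: "A study coordinator, not associated with the surgery, will be the one to introduce the study to the patient in the holding area".

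Allocation is by blocks in RedCap, with the block size undisclosed and no stratification by age, gender or surgery type (8.5.1). Evaluation of blinding is marked as not applicable (8.5.2).

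**The concern.** A double blind needs two things here: the patient must not be able to tell the products apart, and people who know allocations must be kept away from those who recruit, handle or assess patients. A team could follow this protocol to the letter and achieve neither.

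The product limb matters more. The primary endpoint is the Epworth score over days 1 to 14, and sleep hours and awakenings are also reported by the patient through surveys and a diary (Protocol Summary, 3.2.1, 6.1.1). A patient who recognizes the pill can shift those answers with no true effect of melatonin.

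The staffing limb is mainly a threat to allocation concealment. In a blocked sequence, someone who knows the earlier allocations can predict later ones better than chance, and could influence who is approached and when.

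**Working it through.** **1. The plan's own figure.** Section 8.2 gives a difference of 2.65, SD 5.3, two-sided alpha 0.05, 80% power and 64 per arm in each joint cohort.

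n per arm = 2 × (1.960 + 0.842)² × (5.3/2.65)² = 2 × 7.849 × 4 = 62.8, so 63 by the normal formula. The t-test version gives 63.77, so 64. The figure reproduces. Nothing below changes it.

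**2. Do the pills have to match?** Every statement about the product was compared.

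| Section | What it settles | Does it require matching pills? |
|---|---|---|
| 5.1.1 | Two purchases, blank bottles, generic label | No; only the bottle is made alike |
| 5.1.2 | Melatonin is a tablet; placebo ingredients; a pill pack labelled as study drug | No |
| 5.1.3 | Both products are called tablets | Same form implied, appearance not stated |
| 5.2 | Disposal wording covers tablets or capsules | No; leaves even the form loose |

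No section requires a match. Sections 5.1.1 and 5.1.2 also disagree on the container, a blank bottle or a labelled pack.

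**3. Is the code-holder kept from patients?** The three statements on who is unblinded describe one coordinator, a group of randomization staff, and assistants outside the protocol. They could be made to agree only if the coordinator were one of those assistants, which is not stated. The separation in 8.5.1 covers the assistants, not the coordinator who packs bottles. The sentences in 6.2.1 and 11.3.2 cover all study personnel without exception. Section 11.3.2 does not say whether its study coordinator is the unblinded one. Read literally, a person who knows past allocations may help recruit later patients.

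**4. How predictable could allocation become?** Assume a 1:1 permuted block of size 2m, and a recruiter who knows all earlier allocations and the block boundaries and always guesses the arm with more places left. The expected proportion of correct guesses is

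[m + (4^m / C(2m, m) − 1)/2] / (2m).

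- Blocks of 4 (m = 2): [2 + (16/6 − 1)/2]/4 = 2.833/4 = 0.708. Position by position: 0.5 + 2/3 + 2/3 + 1 = 2.833.
- Blocks of 6 (m = 3): [3 + (64/20 − 1)/2]/6 = 4.1/6 = 0.683.

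Chance is 0.50. Both block sizes are assumptions. Because allocation is not stratified by surgery type, separate hip and knee lists would not get in the way of someone tracking the sequence.

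**5. What could a reporting shift do?** This is an illustration on an assumed shift that the documents do not give. Suppose unblinding alone moves the mean Epworth difference by b points. With SD 5.3 and 64 per arm, SE = 5.3 × √(2/64) = 0.937, and the chance of p < 0.05 with no true effect is Φ(b/SE − 1.96) + Φ(−b/SE − 1.96).

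| Assumed shift b | False-positive rate |
|---|---|
| 0 | 5.0% |
| 0.25 | 5.8% |
| 0.5 | 8.3% |
| 1.0 | 18.7% |
| 1.325 (half of 2.65) | 29.3% |
| 2.0 | 56.9% |

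**The case against.** The plan does contain safeguards: blank bottles, restricted knowledge of the codes, an undisclosed block size, RedCap allocation, and randomization run by people outside the protocol. Investigators recruit among their own patients, with eligibility confirmed from records (6.2.1). Describing one coordinator as unblinded suggests that others are blinded. These points stand, and they rule out several stronger readings.

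- *The pills differ.* A reader might infer this from the gelatin and dyes. But the melatonin product's excipients and appearance are not given, and 5.1.3 calls both products tablets. The ingredients cannot show a visible difference. Even with a mismatch, each patient sees one product, and learns the arm only by recognizing it.
- *The code-holder meets patients and cues them.* That the coordinator counts as study personnel is a natural inference, not a stated fact. The cited sentences cover recruitment and consent, before the patient has an allocation to be cued about. Later contact is neither stated nor excluded.
- *Allocation in this trial is 71% predictable.* That figure needs a block size the documents withhold and full knowledge of the ordered sequence.
- *One recognized pill unblinds all of a staff member's later patients.* No section has blinded staff inspect pills, and bottles are expected back empty (5.1.8).

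The safeguards do not answer the two gaps. None of them concerns the pill itself, and none keeps the code-holder out of recruitment.

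**Conclusion.** The concern holds as a gap between the double-blind claim and the procedures meant to deliver it. That no section requires the pills to match rests on the text alone. So does the disagreement over who is unblinded, and the lack of any exemption for that person from the rule on patient contact.

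The consequences are conditional. The documents establish neither a visible difference between the pills nor any actual patient contact by the code-holder. The guess rates are what full knowledge of the sequence and block size would allow, not estimates for this trial. The false-positive rates show sensitivity to an assumed shift and do not predict bias. With blinding evaluation marked as not applicable, the plan would also produce no evidence that the blind had held.

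This should be corrected before the first bottle is issued. It does not affect the sample size.

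**What to change.** - **5.1.2:** require active and placebo to be identical in form, color, size and marking, or over-encapsulated alike, before the first bottle is issued.
- **5.1.1, 5.1.2 and 8.5.1:** name one and the same unblinded role for packing and code-holding. Bar it from recruitment, consent, patient contact, outcome collection and outcome data entry.
- **If the research assistants in 8.5.1 take that role:** move outcome entry and database maintenance to blinded staff. Those assistants now maintain the patient database, so handing them the codes without this change would join code knowledge to control of the data.
- **6.2.1 and 11.3.2:** limit the statement on contact with patients to *all blinded study personnel*.
- **5.1.1 and 5.1.2:** reconcile the two descriptions of the packaging.

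The cost is a small supply expense for matched or over-encapsulated pills and some reassignment among existing staff.
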